C.8.c. Recruitment. The current recruitment strategy is intended to approximate the conditions under which *Anxiety Coach* would have the most impact, i.e. areas where psychiatric needs exceed mental health providers with specialization in CBT for childhood anxiety disorders. To maximize external validity the experimental treatment will be implemented by community therapists recruited from a large geographical area, particularly areas with a mental health shortage designation, and treatment will be paid for through traditional clinical mechanisms.⁷⁸ The principle limitation of the recruitment paradigm is that only patients with access to services will be included in the study. However, this study will establish the safety and efficacy of *Anxiety Coach* with differing levels of therapeutic contact before examining *Anxiety Coach* as a no contact treatment where it would be more difficult to address problems with safety, usability, or lack of progress. We anticipate that the data from the proposed study will prepare for future projects extending services to those outside the system by: a) improving the application; b) documenting the utility of *Anxiety Coach*; and c) creating a web-based portal

through which people in need of treatment could be followed by a provider with whom they have never had face-to-face contact.

C.8.d. Treatment Protocols. For Trials 2 and 3 the guidelines for each intervention instruct the therapist to interact (face-to-face or via the web-portal depending on the condition) once per week for 6 to 12 weeks. Although therapists are not given further instructions on how to deliver *TAU*, the six-session minimum will likely result in a higher level of care than is typically received in real-world settings, since standardization of contact across the interventions is necessary to examine the ability of *Anxiety Coach* to increase provider use of exposure.

C.9. Description of Assessment Measures. In Trial 1 therapists will complete study measures before training, two weeks after training, and then six months later. In Trials 2 and 3, all study measures will be completed at pre- and post-treatment assessment periods except as noted below. Independent evaluators under the supervision of [name] blind to study condition will administer clinician-rated instruments. Therapist, parent and child report will be completed online via the Survey Research Centers electronic survey tools (or by paper and pencil and return via mail if completion electronically is not available).

C.9.a. Clinician-Administered Measures: Anxiety Disorders Interview Schedule for DSM-IV-Child Version Child and Parent Interview Schedules (ADIS-IV-C/P).⁷⁹ The ADIS-IV-C/P are structured interviews to assess the child's symptoms. Diagnoses reflect endorsement of symptoms as well as a severity rating (patient impairment/distress) of at least 4 on a 0-8 scale. The ADIS-IV will be administered in its entirety to the child and the parent together at pre- and post-treatment to determine whether an anxiety disorder is the primary diagnosis and the presence of comorbid diagnoses. Pediatric Anxiety Rating Scale (PARS).⁸⁰ The PARS is a summation of six items assessing anxiety severity, frequency, distress, avoidance, and interference and has been used as the primary continuous outcome measure in treatment studies.³⁰ Clinical Global Impression-Severity and Improvement (CGI-S/I).⁸¹ The CGI-S/I is a 7-point clinician rating of severity of psychopathology and treatment response. The CGI-I will be completed at time 2 and youth receiving a score of 1 ("very much improved") or 2 ("much improved") will be considered treatment responders. Finally, the child and parents will be asked to rate the recent severity of the child's anxiety symptoms on a 0 to 10 scale.

C.9.b. Parent and Child Report Measures. Spence Children's Anxiety Scale (SCAS).^{82,83} This scale measures anxiety symptoms in six areas that correspond with the anxiety disorders in DSM-IV. Child Sheehan Disability Scale (CSDS).⁷⁶ This scale allows the respondent to rate the degree of impairment in the child's and parent's social, school/work and family domains related to anxiety symptoms. Child Avoidance Measure (CAM). This scale allows the respondent to rate how much the child avoids things due to their fears and worries. Therapist Alliance Scale (TAS).⁸⁴ Affect toward the therapist (seven items) and perceived agreement with the therapist regarding tasks of therapy (one item) will be assessed at the end of treatment.

C.9.c. Parent Report Measures. Vanderbilt Assessment Scale (NICHQ) – Parent Informant. This scale is used to measure externalizing symptoms (i.e., ADHD and oppositional defiant disorder). Children's Accommodation Scale (CAS). This form is used to rate how the parent responds to the child's anxiety and distress. Depression Anxiety Stress Scale 21. Parent psychiatric symptoms will be assessed at screening and post treatment with the DASS21. Client Satisfaction Questionnaire-8 (CSQ-8).⁸⁷ Parent satisfaction will be assessed at the end of treatment with this self-report measure provided to the parent through REDCap survey. The modified System Usability Scale plus AC items (mSUSplus; Bangor et al., 2008; Brooke, 2013). Parents will complete the mSUSplus after treatment with anxiety coach.

C.9.d. Child Report Measures. Personal Health Question – 9. The PHQ-9 is a 9-item self-report measure of depressive symptoms over the previous two weeks. Child Automatic Thoughts Scale. This scale measures the frequency of self-reported anxiety provoking thoughts. Child Survey of Coping. This is a self-reporting measure of how the child copes with their fears and worries. Children will rate the severity of their anxiety symptoms on a daily basis using a 11-point scale on the iPod Touch. These report measures will be provided to the child through REDCap survey.

C.9.e. Therapist Report Measures. The survey, conducted under IRB 14-002608, will be an adaptation of the measures used in a previous study¹⁵ and will inquire about demographic/practice information. Therapists will be asked to indicate whether or not they have used various interventions over the past 12 months with anxious children and adolescents (presented separately). Additionally, therapists will be asked about their beliefs about exposure. Therapists that provide study treatment will complete the exposure beliefs questionnaire again before and after treatment. The modified System Usability Scale plus AC items (mSUSplus; Bangor et al., 2008; Brooke, 2013). Therapists in all 3 trials will complete the mSUSplus. Therapist in Trial 1 will complete the SUS two weeks and six months after training. In Trials 2 and 3 therapists will complete the SUS as part of the post treatment measures.

C.9.f. Session Coding. All therapy sessions in the TAU and FTF-AC will be audio recorded and coded with a CBT for child anxiety Treatment Adherence scale that has been used in previous treatment studies,^{18,67,74} in addition to recording the amount of time spent planning and conducting exposure. Audio recording will be used rather than video, as it will be easier to set-up and transport if exposures are completed outside of the office. Electronic communication between therapists and patients will be automatically recorded and phone conversations will be summarized in writing. These contacts will also be coded for recommendations regarding exposure. 10% of sessions will be coded by two evaluators independently to examine inter-rater reliability.

C.9.f.2 Electronic Data. All use of the Anxiety Coach system (desktop or mobile device applications) is automatically recorded. This data will include anxiety ratings, fear ladder items, and details on completed exposures. These data will be extracted to assess use of the system in all three trials. In all three trials therapists will be given a study name (i.e. T1therapist1) in the Anxiety Coach system. In Trial 1, therapist will be given access to Anxiety Coach for 1 year following the training. They will be free to use the system in their practice as they choose. Although the system is secure, therapist will be instructed that because it is in development that patient names should not be entered. As such, the system will automatically assign patient identifiers (e.g., Patient #1). In Trials 2 and 3, enrolled patients will be given a study name (i.e. T2patient1).

C.9.g. Therapist Support. The frequency and content of communication between the project director and therapists will be recorded. All electronic communication within Anxiety Coach will be automatically saved within the web-based portal and the duration and content of phone conversations or standard electronic communication will be logged.

C.9.h. Rater Training and Integrity. Clinician rated measures will be completed by independent evaluators (IEs) blind to the study hypotheses under the supervision of [name], who will ensure that evaluations are completed accurately and thoroughly. Therapy session recordings will be coded by a separate IE blind to the study hypotheses and assessment results. [name] will lead training of the independent evaluators in assessment and coding including ratings of criterion tapes and review of practice assessments. Raters will be expected to score within 15% of [name] ratings on criterion cases. [name] will review 10% of assessments and session codings completed by the IEs in the beginning of the study and those whose scores fall outside of the 15% range will not conduct evaluations until this level of agreement is achieved. After competency has been established [name] will review 5% of assessments and sessions codings. [name] will review assessment and coding discrepancies between the IEs and [name] during the study to reduce the effect of bias. All assessments done by the IE via videoconference will be audio recorded so [name] and [name] can ensure that the evaluations are completed accurately and thoroughly.

C.9.i. Qualitative Measures. [name] will work with [name] to identify questions and topics for a semi-structured interview script. The script will be pilot-tested to ensure that questions and follow-up probes are easily comprehended and delivered in a sensitive manner. The semi-structured script will follow guidelines for minimizing bias and increasing the reliability and validity of interview data.^{90,91} The interviews will be conducted by an experienced qualitative interviewer not involved with the patients' medical care or development of *Anxiety Coach* or the treatment protocols. All interviews will be audio-recorded

C.10. Data Management and Statistical Considerations

C.10.a. Data Analytic Plan. Time has been budgeted for a Master-level statistician. The activities of the individual will be coordinated by the doctoral-level statistician dedicated to the Department of Psychiatry and Psychology under the ultimate direction of the [name]. The MS statistician will assume the primary responsibility of implementing the statistical analysis plan and completing standard statistical summaries of the study data. As this is a feasibility study and not powered to examine the statistical significance of group differences, the statistical analysis will be primarily descriptive in nature.

C.10.b. Tests of Specific Aims

C.10.b.1. Aim 1: Adapt *Anxiety Coach* for use with a health care provider. Data from an open trial of 15 patients treated with *Anxiety Coach* and the web-based portal in FTF-AC or MC-AC (7 to 8 per condition) will be analyzed descriptively. Quantitative data regarding adherence (accessing the application at least 50% of days) and improvement (symptom change) will be examined to ensure that patients are utilizing and benefiting from treatment. For qualitative data, themes regarding usability and treatment satisfaction will be identified and a coding strategy will be developed. Analysts with experience in qualitative data analysis will code interviews using methods of content analysis (i.e., systematic process of sorting and coding information based on themes).^{92,93} QSR's NVivo 9 (QSR International, Doncaster, Victoria, Australia; NVivo 2010) qualitative data software analysis program will be used to facilitate data coding and sorting. The open trial will be monitored for adverse events, which will be addressed appropriately. Data from the therapist survey will be evaluated descriptively (i.e., frequency of endorsement of therapeutic strategies and attitudes toward exposure).

C.10.b.2. Aim 2: Assess feasibility, safety, acceptance, and impact of *Anxiety Coach*. Analyses for Trial 1 will consist of examining changes in therapist questionnaires via repeated measures analyses of variation and descriptively summarizing data on therapist use and ratings of acceptability. Most appropriately for the present design of Trials 2 and 3, descriptive statistics will be calculated on all fidelity (e.g., frequency of exposure), feasibility (e.g., quantity and content of communication between the therapist and project director, frequency of assessing the application), and clinical variables (e.g., means, standard deviations, percentage of patients continuing to meet diagnostic criteria). Consistent with the ultimate goal of generating estimates of the effect of *Anxiety Coach*, symptom change within Trials 2 and 3 will be compared between groups using repeated measures analysis of variance (RMANOVA) and the frequency of the therapists' use of exposure will be compared between the TAU and FTF-AC condition using analysis of covariance (ANCOVA) to control for diagnosis and symptom severity. Given that this project aims to test the feasibility of a fully powered RCT, analyses testing group differences will be considered exploratory. Although the use of RMANOVA and ANCOVA has significant limitations (i.e., the treatment of missing data), the small sample size and inclusion of multiple therapists does not permit the use of a more powerful statistical approach such as a mixed-effects regression model. However, exploratory analyses using mixed-effects regression model will be conducted. These analyses will be completed to assist in planning design and analysis of a fully powered RCT, rather than to provide interpretable results.

C.10.b.3. Aim 3: Develop a protocol for implementing *Anxiety Coach*. To develop a protocol for using *Anxiety Coach* to increase therapist fidelity to evidence-based CBT and provide treatment with minimal direct contact, the frequency and timing of contact between the project director and therapists as well as the therapist and patient will be used to construct guidelines for monitoring and interacting with therapists and patients. The questions from patients and therapists will be summarized qualitatively and used to refine *Anxiety Coach* and develop the educational component of the protocol.

C.10.c. Attrition, Noncompliance and Missing Data. The intention to treat analysis set will serve as the principal analysis set. Attempts will be made to minimize the missing data due to missed visits (i.e., fewer than the required six appointments). To handle missing data the following approach will be used. The analyses of the primary outcome will be performed in two ways: 1) using complete case scenario i.e., those patients that

July 1, 2019 (Version 12)

have data available on both time points and 2) imputing a rank from the earlier time point carried forward. Last rank carried forward has been shown to have better statistical properties than the last observation carried forward approach. In addition to these, we will also explore other sensitivity analysis such as imputation of a mean or median or worst or best case values in the respective groups. Findings from sensitivity analysis will be viewed in light of primary analysis prior to reaching final conclusions and interpretation of the results.

PROTECTION OF HUMAN SUBJECTS

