Trial 3. In Trial 3 (Increasing Access) children with anxiety disorders will be randomized to receive with MC-AC delivered by therapists in the Pediatric Anxiety Disorders Clinic (study staff) or treatment as usual in the community or within Mayo Clinic, just not with their current therapist. Data collection will include questionnaires completed by therapists, patients, and parents before and after treatment, as well as data automatically saved by the application. Following the study all patients will be offered treatment within the Pediatric Anxiety Disorders Clinic. Patients in the community treatment group will also receive the Anxiety Coach application.

C.3.c. Phase III: Revision Stage (4 months). During the final 4 months the feasibility data will be analyzed along with feedback from patients and therapists. This data will be used to revise the protocol for training therapists to use *Anxiety Coach*, prepare a manuscript for publication, and apply for R01 funding to conduct a fully powered randomized controlled trial to evaluate the symptom improvement and cost-efficiency of using *Anxiety Coach* to provide minimal contact care and disseminate evidence-based treatment.

C.4. Participant Availability and Recruitment. The outpatient mental health therapists in Trial 2 will be recruited and will subsequently recruit their own patients into the study. The therapists will be provided an iPod Touch for participating in the study that they can keep. Before recruiting patients, therapists will complete appropriate training in research ethics. Patients will be recruited by the therapists during their initial evaluation. Patients will be screened and consented by study staff. Patients **and therapists** in each condition will be reimbursed for completing study assessments and recordings (\$100 total) and will receive an iPod Touch that they can keep. Partnering institutions in the minimal contact condition can be reimbursed for non-billable time spent on the *Anxiety Coach* portal at a rate of \$146.34 per hour up to 6 hours. The therapists for Trial 1 have largely been recruited under the initially approved IRB protocol. Additional therapists will be recruited as needed.

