C.5.e. Treatment as usual (TAU). The control condition in Trial 3 will consist of having the family participate in the existing clinical services offered by the therapist over the 12-week period. After 12-weeks they will be asked to sign a release of information to have the any outside treatment records sent for review by the study staff. The records will be coded for treatment components. As the post-study evaluations, patients in the TAU condition will receive Anxiety Coach and be offered additional treatment as needed.

C.6. Design Considerations

C.6.a. Justification of Experimental Design. The use of three conditions across two trials allows for an examination of the effects of *Anxiety Coach* and direct therapist contact. Specifically, the **TAU vs. FTF-AC comparison** provides an estimate of the feasibility and palatability of *Anxiety Coach* to therapists, a measure

of the extent to which the application facilitates therapists' use of exposure-based methods, the usefulness of *Anxiety Coach* for disseminating evidence-based CBT methods to community therapists, and its value for facilitating treatment adherence among patients with anxiety disorders. Randomizing therapists/patients to one of two conditions removes the potential for bias to affect recruitment, keeps the evaluators blind to experimental condition, removes concerns with order effects, and allows for the more patients to be treated simultaneously thus decreasing the length of the study. **The MC-AC vs. TAU comparison** provides an estimate of the feasibility as well as the impact on acceptability and outcome of using *Anxiety Coach* with limited direct therapist contact as a method for extending treatment outside of the brick and mortar mental health settings. To increase the real-world generalizability of the study, the study will not pay for therapy, but patients in all conditions will be reimbursed for participation in assessments and will be allowed to keep the iPod Touch.

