If therapists in Trial 1 choose to use Anxiety Coach in their practice during, those patients will not be engaged in any research activities. In order to use the application the patient must agree to the terms of use that explain what data Mayo Clinic collects and how these data are used.

C.7.e. Treatment Assignment. For Trial 2, therapists will be randomized to either TAU or FTF-AC after they are consented. The therapist will then offer participation to the next patient they see likely to qualify. (If needed, the second patient treated by a therapist randomized to TAU will be enrolled in the FTF-AC condition.) This format clearly differentiates the therapists' participation in the study from the patients' participation. To limit bias in enrollment, neither patients nor the independent evaluators will be aware of therapeutic condition at the time of enrollment. Treatment in each condition can begin within 1 to 2 weeks of the evaluation as soon as the patient has completed the study evaluation. All patients will be informed that participation in the study includes the possibility of enrollment into either of two conditions. If patients discontinue treatment prematurely, before the sixth session, they will not be replaced with another patient. Instead efforts will be made to complete early withdrawal post-treatment evaluations on all enrollees and the frequency of premature discontinuation will be compared between conditions. For Trial 1, the therapists will have access to the Anxiety Coach application and can use it as they choose in their clinical practice. For Trial 3, treatment assignment will occur following consent and the pre-evaluation is completed.

C.7.f. Therapists, Treatment Integrity and Competence. Therapists in Trials 2 and 3 will provide treatment. To determine the success of creating conditions with distinct therapist behavior, all sessions and communication in each condition will be recorded and coded for use of exposure and other interventions. In the TAU condition, the therapist will not receive any instruction regarding the content of treatment. In all three conditions across the two trials the intervention specialists or the PI will monitor and support the therapists' compliance with guidelines. The intervention specialists have highly developed therapeutic skills, at least five years' experience providing CBT to children with anxiety disorders and their families, extensive one-on-one

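### In Trial 3 the release for outside treatment records is sought only after 12 weeks, so controls who cannot be reached or who refuse by then may have no data on what usual care contained

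*Protocol*

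**What the plan says.** Protocol C.3.b (Trial 3) places the control child's care in "treatment as usual in the community or within Mayo Clinic, just not with their current therapist". For data sources it says: "Data collection will include questionnaires completed by therapists, patients, and parents before and after treatment, as well as data automatically saved by the application". Session audio is not on that list, although the Trial 2 paragraph just above it does include audio.

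Protocol C.5.e gives the route to the content of control-arm care: "After 12-weeks they will be asked to sign a release of information", so that study staff can obtain and review records of outside treatment. It adds: "The records will be coded for treatment components". No release is described at consent (C.7.d) or at early withdrawal (C.7.e).

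For the app, C.9.f.2 states: "All use of the Anxiety Coach system (desktop or mobile device applications) is automatically recorded".

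Two other sections bear on session recording. C.7.f, in a paragraph that opens with Trials 2 and 3, says "all sessions and communication in each condition will be recorded and coded for use of exposure and other interventions". C.9.f says "All therapy sessions in the TAU and FTF-AC will be audio recorded and coded", without limiting usual care to Trial 2.

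C.10.b.2 plans descriptive statistics for Trials 2 and 3 on fidelity variables, with frequency of exposure as its example. The SAP says nothing about usual-care content or the records release.

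**The concern.** Trial 3 compares minimal-contact Anxiety Coach with whatever care the control family obtains. To interpret the contrast, and to carry it into the planned larger trial, one needs to know how much treatment controls received and how much of it was exposure. C.6.b recognises the same issue for the face-to-face comparison: exposure within usual care can dilute the effect, and recording and coding the sessions is part of the answer. In Trial 3 retrospective records appear to take the place of that safeguard.

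The permission for those records is sought at the end of the 12 weeks, when contact is most likely to have been lost. Missingness in the control arm may then depend on whether the family stayed engaged. No comparable permission step governs the app log in the other arm. At stake are the descriptive figures on control-arm exposure and sessions attended, and any Trial 3 comparison of premature discontinuation, which C.7.e defines by the sixth session.

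**Working it through.** The documents give no loss rate, power or precision figure on this point, so there is nothing to reproduce. The check has two parts.

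**1. Is there another source for what usual care contained?**

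- *Symptom and diagnostic measures (C.9.a to C.9.d):* these cover diagnosis, severity, impairment, alliance, satisfaction, usability and related scales. None is described as recording treatment components or sessions attended.
- *Therapist measures (C.9.e):* these cover the survey of general practice, beliefs about exposure, and usability. C.3.a.4 says Trial 3 treatment is given by study-staff therapists, and enrolment of the controls' outside therapists is not described.
- *Daily iPod ratings (C.7.g, C.9.d):* symptom severity only.
- *Early-withdrawal evaluation (C.7.e) and continued assessment after early termination (4.1.2.b):* these would collect the same measures, not treatment content.
- *Session recording:* C.7.f and C.9.f, read literally, would include Trial 3 usual care. The Trial 3 paragraph of C.3.b lists no audio, and C.5.e relies on records. The four sections cannot all stand as written.
- *Care within Mayo Clinic:* C.5.e describes the release for outside records only, so in-house records may not depend on it.

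Unless the recording statements really do extend to Trial 3 controls, outside records are the only described source for children treated outside Mayo Clinic.

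**2. How much could missing records matter?**

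Inputs:
- Trial 3 has 30 patients (Specific Aims, Aim 2).
- Controls: n = 15, **assuming** a 1:1 split; the ratio is not stated.
- Share with no release obtained: d = 10% to 30%, **assumed**; no rate is given.
- For simplicity, all 15 controls are treated as depending on outside records.

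Expected number without records = n × d. Chance of at least one = 1 − (1 − d)^15.

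| d | Expected without records | Chance of at least one |
|---|---|---|
| 10% | 15 × 0.10 = 1.5 | 1 − 0.90^15 = 79% |
| 20% | 15 × 0.20 = 3.0 | 1 − 0.80^15 = 97% |
| 30% | 15 × 0.30 = 4.5 | 1 − 0.70^15 = over 99% |

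Suppose m controls have no records and x of the other 15 − m received exposure. The true share lies between x/15 (none of the m had exposure) and (x + m)/15 (all of them did). The width is m/15, whatever x is:

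- m = 2: 2/15 = 13 percentage points
- m = 3: 3/15 = 20 percentage points
- m = 4: 4/15 = 27 percentage points

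This is a width of uncertainty. It does not show in which direction an estimate from the available records would err.

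**The case against.** A reader might infer that care is simply unknown for every control family that withdrew. The documents do not support that. C.5.e does not restrict the request to families still in the study. A release signed at week 12 can return records for the whole period, including the last session. Stopping therapy is also not the same as leaving the study: C.7.e plans early-withdrawal evaluations on all enrollees (in a paragraph mainly about Trial 2), and 4.1.2.b lets early terminators go on giving assessment data. Only families who are out of reach or who refuse are affected.

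A reader might also infer that usual care will look fuller and better attended than it was. That is plausible but not shown; if families without records had more exposure than the others, the error would run the other way. Nor is the loss necessarily permanent, since clinical records exist and nothing bars a request at another time.

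The app log should not be treated as complete. Nothing is logged once a child stops using the app, phone contacts are summarised by hand (C.9.f), users may decline research use of their data (4.1.2.b), and the SAP describes exposures recorded inaccurately for technical reasons.

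Finally, the study is descriptive and unpowered (C.10.a), and group tests are exploratory (C.10.b.2). The planned ANCOVA of exposure frequency compares usual care with the face-to-face app condition, which is Trial 2. Missing control content therefore limits the reading of Trial 3 but does not prevent it.

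All of this stands, and it bounds the point. It does not supply a route to treatment content for outside-treated controls who are lost or refuse by week 12. Recording why data are missing, which 4.1.2.b does promise, does not replace the data.

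**Conclusion.** The concern holds as a risk of selective missing data in the Trial 3 control arm. The release is requested only after 12 weeks, and for controls treated outside Mayo Clinic no other source of treatment content or session count is clearly described. Ascertainment can differ between the arms; the direction of any bias is not known.

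Under the stated assumptions, 2 to 4 controls without records leave the share who received exposure uncertain by 13 to 27 percentage points. That is material for a descriptive estimate meant to inform a larger trial, but it does not overturn any planned inference.

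Separately, and without any assumption, C.7.f and C.9.f conflict with C.3.b (Trial 3) and C.5.e on whether Trial 3 usual-care sessions are recorded. The change is worth making because it is cheap and acts before contact can be lost.

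**What to change.** 1. Ask every Trial 3 family for the records release at the consent and evaluation visit, before assignment, to cover the following 12 weeks. Asking all families also keeps the request from signalling the arm.
2. Have the study coordinator, not the blinded evaluator, add the provider's name once care is arranged.
3. If the release is still unsigned, ask again at any early-withdrawal evaluation.
4. At 12 weeks, request records for all controls who signed and did not revoke, including those who stopped treatment.
5. Report how many controls have records, and code treatment content for the rest as unknown.
6. Reconcile C.3.b (Trial 3), C.5.e, C.7.f and C.9.f so that the statement on recording all sessions covers only the arms where sessions are recorded.

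The cost is one extra form for all families at a visit that already takes place, plus a short call to add the provider. Some releases will have to be completed later because the provider is not known at consent, and refusal or revocation remains possible. If Trial 3 collection is already over, items 5 and 6 can still be done.
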